### 12.4.3 Analysis of the Secondary Endpoint(s)

The main secondary endpoint of interest is sleep duration. Paired-samples t-tests will be used to compare differences in repeated measures of sleep duration (baseline and intervention). Mean sleep duration will be calculated as a weighted mean using the formula [(weekday sleep duration x 5) + weekend sleep duration x 2)]/7. Weekday nights will be Sunday through Thursday nights; weekend nights will be Friday and Saturday nights. The primary secondary outcome for sleep duration data will be obtained from the two-week baseline sleep dairy data and the last two weeks of intervention sleep diary data. Other secondary endpoints that will be compared between baseline and intervention using paired sample t-tests include measures for 1) diet quality (defined as the percentage of fat, percentage of carbohydrate, and total caloric intake estimated from the ASA24 at baseline and intervention), 2) physical symptoms (estimated from SAFTEE Questionnaire), 3) cigarette and alcohol use estimated from the Demographics-SDOH: Alcohol use (AUDIT C), Demographics - SDOH: Tobacco use, 4) affective well-being (estimated from 36-item Short Form Health Survey (SF-36) version 1) self- regulation (estimated from the Index for Self-regulation), 6) physical activity (defined as moderate/vigorous [100-429 millgravity units] and light [10-99 millgravity units]) estimated from the twoweek baseline accelerometry data and the last two weeks of the intervention accelerometry data, and 8) sedentary behavior (defined as less than 10 millgravity units) estimated from the two-week baseline accelerometry data and the last two weeks of the intervention accelerometry data.

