#### 3.2.2 Secondary Study Endpoints

Secondary endpoints will be evaluated by pre- and post-intervention sleep duration, physical activity, sedentary behavior, diet quality, smoking, alcohol use, affective well-being, morning fatigue, evening fatigue, and self- regulation measurements. These secondary endpoints were chosen to gain preliminary evidence of relationships between SASI and sleep duration, MetS risk behaviors, as well as symptoms associated with MetS risk behaviors, and self-regulation. Elucidating these relationships will inform potential pathways through which SASI impacts MetS.

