- The ASA24 (ASA24-2016) is a freely available web-based tool designed to collect self-report dietary recall data. While under- reporting and inaccuracy in self-report of dietary intake is a known limitation, 24-hour recalls provide more accurate data than other screeners or food frequency questionnaires, and the ASA24 has demonstrated similar criterion validity against actual food intaketo other more complex and time consuming recall methods.
- Demographics SDOH: Alcohol use (AUDIT C)
- Demographics SDOH: Tobacco use
- Index of Self-Regulation
- SAFTEE questionnaire
- PROMIS-Depression 6a
- End of study surveys at home (week 15) o 36-item Short Form Health Survey (SF-36) version 1
  - o ASA24
    - The ASA24 (ASA24-2016) is a freely available web-based tool designed to collect self-report dietary recall data. While under-reporting and inaccuracy in self-report of dietary intake is a known limitation, 24-hour recalls provide more accurate data than other screeners or food frequency questionnaires, and the ASA24 has demonstrated similar criterion validity against actual food intaketo other more complex and time consuming recall methods.
  - Demographics SDOH: Alcohol use (AUDIT C)
  - Demographics SDOH: Tobacco use
  - o Index of Self-Regulation
  - o o SAFTEE questionnaire
  - PROMIS- Depression 6a
- Intervention surveys at home (weeks 1-15) Epworth Sleepiness Scale (weekly) PROMIS Fatigue 6a morning (weekly) PROMIS Fatigue 6a evening (weekly) Sleep Diary (daily)

**Objective Sleep and Physical Activity Measures.** Participants will wear a wrist accelerometer 24/7 for 14 continuous days during the first 2 weeks of baseline data collection and the last 2 weeks of the SASI intervention. The accelerometer may be removed for bathing and contact sports. Data collected from the accelerometer will be used to estimate sleep duration and physical activity levels. A wrist worn fitbit will also be worn during the 2-week baseline and 12 week SASI intervention by the study by participants.

Objective OSA Measures. Participants being treated for OSA will wear a pulse oximeter on their fingertip for one night during the first 2-week baseline data collection.

**Training and Treatment Fidelity**: SASI facilitators will be individuals with prior training and experience delivering sleep interventions. Facilitators will complete training in intervention content and telephone

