## 12 Statistical Considerations

## 12.1 Statistical and Analytical Plans

A formal SAP will be developed for this study in consultation with the study biostatistician. Only a general overview of study statistics is included in this protocol.

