## 12.2 Statistical Hypotheses

The sample size is too small to make inferences about relationships evaluated in the pilot study to the larger population of middle aged adults with MetS. For the primary aim, acceptability will be evaluated by the percentage of participants rating SASI as acceptable (overall acceptability survey scores greater than 21), neutral (overall acceptability survey scores equal to 21), and unacceptable (overall acceptability survey scores less than 21) on the Acceptability Survey at each of two time points (pre-intervention and post intervention). Feasibility will be evaluated by the 1) recruitment rate: the percentage of potential participants screened in order to enroll 60 participants with evaluable data, 2) attrition rate: the percentage of enrolled participants completing the 18-week study. Participants will be considered withdrawn after 4 weeks of not responding to phone calls/emails during the intervention, and the 3) protocol adherence rates; the percentage of participants completing greater than or equal to 4 daily sleep diary entries per week for 80% or more of the intervention period. For the secondary endpoints, paired t-tests will be used to compare the mean preintervention and mean post-intervention estimates for SAFTEE scores, physical activity, sedentary behavior, diet quality, smoking, alcohol use, affective well-being, morning fatique, evening fatique, and self- regulation measurements. For the exploratory endpoints of perceived barriers and facilitators of SASI, bivariate correlations between specific socio-ecological factors and sleep duration change will be identified. The qualitative data from the post intervention interviews will be analyzed using content analysis. Content analysis includes a line- by-line review that yields clusters of data that are coded. This coding is linked to interview questions. Summarization of coding will be performed across individual interviews, and subsequently crossclassified to yield a rich descriptive analysis. Emerging themes within and across interviews will be identified, and review of fit with data verified.

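### The moderate/vigorous activity band is closed at 429 milligravity and nothing covers 430 or more, so harder exercise can be scored as a fall in activity

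*Combined protocol and SAP*

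**What the plan says.** Physical activity and sedentary behavior are named secondary endpoints in Section 3.2.2: "Secondary endpoints will be evaluated by pre- and post-intervention sleep duration, physical activity, sedentary behavior, diet quality". That section gives no intensity limits. Section 6.1.1, in its paragraph on objective sleep and activity measurement, says only that "Data collected from the accelerometer will be used to estimate sleep duration and physical activity levels".

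The limits appear once, in Section 12.4.3. Activity is "physical activity (defined as moderate/vigorous [100-429 millgravity units] and light [10-99 millgravity units"), and the complement is "sedentary behavior (defined as less than 10 millgravity units"). Both endpoints are taken from the two-week baseline recording and the recording in the last two weeks of the intervention. They fall under the general rule of that section: "Other secondary endpoints that will be compared between baseline and intervention using paired sample t-tests include measures for" the items listed.

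Section 12.1 states that "A formal SAP will be developed for this study in consultation with the study biostatistician". No such text is among the documents, so Section 12.4.3 is the only operative definition.

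**The concern.** A band that claims to hold vigorous movement, and is the highest band in the scheme, would be expected to have no ceiling. Here it has one, while the sedentary band at the other end is open. Either the ceiling is a slip, or 429 was meant as the line between moderate and vigorous effort and the vigorous band was left out.

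Both readings have the same consequence for an analyst who follows the text. The endpoint no longer rises with activity: a person who exercises harder moves minutes out of the scored category. For such a person the pre-post difference that enters the paired t-test is too small and can have the wrong sign. Physical activity is one of the MetS risk behaviors on which the secondary objective seeks preliminary efficacy, and Sections 1.1 and 1.2 say the pilot data will feed a fully powered randomized trial. A misscored change would be carried into that planning.

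**Working it through.** The plan states no numerical result for this endpoint, so there is no figure to reproduce. The check has two parts: whether the bands cover all values, and what the gap does to a pre-post difference.

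**Coverage of the bands as written (Section 12.4.3)**

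| Value (milligravity) | Band |
|---|---|
| 9 | sedentary |
| 10, 99 | light |
| 99.5 | none |
| 100, 429 | moderate/vigorous |
| 430, 600, 1000 | none |

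The first uncovered whole number is 430, and everything above it is uncovered. Values between 99 and 100 are also unassigned, but only if the data are not rounded to whole numbers.

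**Effect on the change score**

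Let *M* be minutes per day at 100 or more, and *V* the minutes per day above 429.

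- Scored time under the written band: *W* = *M* − *V*
- Change from baseline: Δ*W* = Δ*M* − Δ*V*

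The error in each participant's change is therefore −Δ*V*, and the error in the group mean change is minus the mean of Δ*V*. The sign is reversed whenever Δ*V* > Δ*M* > 0.

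**Illustrations (assumed profiles, minutes per day)**

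1. Total active time fixed at 30 min, with some of it shifted from the 100–429 range to 430 or above:

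| Minutes shifted | Written band | Open-ended band |
|---|---|---|
| 0 | 30 | 30 |
| 5 | 25 | 30 |
| 10 | 20 | 30 |
| 15 | 15 | 30 |
| 20 | 10 | 30 |
| 30 | 0 | 30 |

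The last row is the participant who replaces 30 min at about 400 units with 30 min at about 450: the score shows a loss of 30 min/day.

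2. Baseline 30 min at 200 units; post-intervention 20 min at 200 plus 20 min at 500. Here Δ*M* = 40 − 30 = +10 and Δ*V* = 20 − 0 = +20, so Δ*W* = 10 − 20 = −10. The written band goes from 30 to 20 and the open-ended band from 30 to 40.

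3. A participant who adds 30 min/day above 429 and changes nothing else has Δ*M* = Δ*V* = 30, so Δ*W* = 0.

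**Search for a rule elsewhere**

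Sections 3.2.2, 6.1.1 and 12.2 name physical activity without intensity limits. Section 12.4.1 provides for a general look at erroneous outliers but sets no accelerometer ceiling and does not class values of 430 or more as artefact. Nothing in the documents fills the gap.

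**The case against.** The wording gap is hard to dispute; the case against concerns its weight.

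- **Size is unknown and may be small.** The documents give neither the share of time above 429 nor the epoch over which acceleration is averaged. In short sleepers aged 35 to 60 with metabolic risk factors, sustained values that high may be rare. This stands: the profiles above are assumed, and the bias exists only where time above 429 changes.
- **The stakes are modest.** Acceptability and feasibility are primary, and sleep duration is the main secondary endpoint. Section 12.2 concedes that "The sample size is too small to make inferences about relationships evaluated in the pilot study" to the wider population, and Section 12.4.7.2 disclaims any evaluation of efficacy. No success criterion uses activity. This limits severity, but the Protocol Summary still lists preliminary efficacy on activity as an objective, and a descriptive estimate should also have the right sign.
- **A later SAP may complete the definition.** Possible, but it cannot be checked. What is written is a definite rule that misscores, not a detail left open.
- **The list may have lost an item.** The numbering in Section 12.4.3 skips 5 and 7, the latter between activity and sedentary behavior. Whether a vigorous band stood there cannot be told.
- **An open top band could admit device artefact.** This is a fair caution about the remedy. It calls for a separate artefact rule; a ceiling on the activity category is not a substitute for one.
- **The 99-to-100 gap is trivial.** Agreed: rounding closes it. Contiguous limits remove it at no extra effort.

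**Conclusion.** The concern holds. As written, Section 12.4.3 leaves every value of 430 milligravity or more outside all categories, although its top category is named moderate/vigorous. The scored change for each participant is off by exactly the change in time spent above 429, in the direction that makes more vigorous people look less active. It can reverse the sign of an individual change.

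The size at group level cannot be given from the documents. It is nil if nobody exceeds 429 at either assessment or if that time does not change on average; otherwise it equals the mean change in that time. The conclusion rests on reading the bands literally and on there being no other definition in force. Because this is a secondary endpoint of a pilot and the recordings can be re-cut, it should be corrected before analysis but does not threaten the primary aims.

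**What to change.** In Section 12.4.3, and in the formal SAP when it is written, define contiguous bands with an open top: sedentary below 10, light 10 to below 100, moderate/vigorous 100 or more. If 429 was meant to separate moderate from vigorous effort, report moderate (100 to below 430) and vigorous (430 or more) as sub-bands and take their sum as the endpoint. If it was meant as an artefact limit, say so in a separate data-cleaning rule, so that device spikes are screened out without removing real vigorous movement.

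The cost is a line of text, plus a short artefact rule if one is wanted. The same accelerometer files serve, with no new data, visits or participant burden. Settling the definition before the post-intervention data are examined also avoids a choice of cut points made with the results in view.

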### 12.4.4 Safety Analyses

As this study is minimal risk, it is not anticipated that the study may be halted. However, if there is a determination of unexpected, significant, or unacceptable risk to participants, the study may be temporarily suspended or prematurely terminated.

### 12.4.5 Adherence and Retention Analyses

Adherence and retention are the primary endpoints for this pilot study.

### 12.4.6 Baseline Descriptive Statistics

Baseline characteristics, including demographic and clinical characteristics of the sample, using descriptive statistics will be compared between participants for whom the intervention was acceptable and for whom the intervention was unacceptable at each time point (pre-intervention and post- intervention). Inferential statistics will not be used.

## 12.4.7 Planned Interim Analysis.

The research coordinator will prepare weekly reports on participant demographics, recruitment, attrition, and protocol adherence. The statistician will prepare monthly reports about missing, invalid, or inconsistent data on selected key variables. The reports will also contain a summary of monthly accrual and cumulative accrual,

Version Date: September 27, 2019

a summary of key characteristics of the study participants, and a summary of the completeness and quality of

data.

### 12.4.7.1 Safety Review

As this study is minimal risk, it is not anticipated that the study may be halted. However, if there is a determination of unexpected, significant, or unacceptable risk to participants, the study may be temporarily suspended or prematurely terminated.

### 12.4.7.2 Efficacy Review

This study will not evaluate efficacy.

### 12.4.8 Additional Sub-Group Analyses

Primary or secondary endpoints may be analyzed for descriptive purposes by age, race/ethnicity, or any other participant characteristic as described in detail in the SAP.

## 12.4.9 Multiple Comparison/Multiplicity

Not applicable.

### 12.4.10 Tabulation of Individual Response Data

For these analyses, the investigators will generally not control for multiple comparisons.

## 12.4.11 Exploratory Analyses

Explore the perceived barriers and facilitators of SASI (e.g., socio-ecological factors).

### 12.5 Sample Size

Our final sample size is N=60. To achieve this, it is anticipated that 220 interested potential participants will go through the telephone screening procedures. The reason we will need to screen 220 is because OSA is often a co-morbid condition with MetS and we anticipate 65% of participants screened will become ineligible after the initial CTSI visit. We also anticipate that 20% will not complete the study protocol.

#### 12.6 Measures to Minimize Bias

## 12.6.1 Enrollment/Randomization/Masking Procedures

Not applicable.

## 12.6.2 Evaluation of Success of Blinding

Not applicable.

## 12.6.3 Breaking the Study Blind/Participant Code

Not applicable.

### 13 Source Documents and Access to Source Data/Documents

Source data is all information, original records of clinical findings, observations, or other activities in a clinical trial necessary for the reconstruction and evaluation of the trial. Source data are contained in source documents. Examples of these original documents, and data records include: hospital records, clinical and office charts, laboratory notes, memoranda, subjects' diaries or evaluation checklists, pharmacy dispensing records, recorded data from automated instruments, copies or transcriptions certified after verification as being accurate and complete, microfiches, photographic negatives, microfilm or magnetic media, x-rays,

Version Date: September 27, 2019

subject files, and records kept at the pharmacy, at the laboratories, and at medico-technical departments

involved in the clinical trial.

The study case report form (CRF) is the primary data collection instrument for the study. All data requested on the CRF must be recorded. All missing data must be explained. If a space on the CRF is left blank because the procedure was not done or the question was not asked, write "N/D". If the item is not applicable to the individual case, write "N/A". All entries should be printed legibly in black ink. If any entry error has been made, to correct such an error, draw a single straight line through the incorrect entry and enter the correct data above it. All such changes must be initialed and dated. DO NOT ERASE OR WHITE OUT ERRORS. For clarification of illegible or uncertain entries, print the clarification above the item, then initial and date it.

Access to study records will be limited to IRB-approved members of the study team. The investigator will permit study-related monitoring, audits, and inspections by the IRB/EC, the sponsor, government regulatory bodies, and University compliance and quality assurance groups of all study related documents (e.g. source documents, regulatory documents, data collection instruments, study data etc.). The investigator will ensure the capability for inspections of applicable study-related facilities (e.g. pharmacy, diagnostic laboratory, etc.).

Participation as an investigator in this study implies acceptance of potential inspection by government regulatory authorities and applicable University compliance and quality assurance offices.

# 14 Quality Assurance and Quality Control

QC procedures will be implemented beginning with the data entry system and data QC checks that will be run on the database will be generated. Any missing data or data anomalies will be communicated to the site(s) for clarification/resolution.

Following written SOPs, the monitors will verify that the clinical trial is conducted and data are generated, documented (recorded), and reported in compliance with the protocol, GCP, and the applicable regulatory requirements (e.g., Good Laboratory Practices (GLP), Good Manufacturing Practices (GMP)).

The investigational site will provide direct access to all trial related sites, source data/documents, and reports for the purpose of monitoring and auditing by the sponsor, and inspection by local and regulatory authorities.

# 15 Ethics/Protection of Human Subjects

### 15.1 Ethical Standard

The investigator will ensure that this study is conducted in full conformity with Regulations for the Protection of Human Subjects of Research codified in 45 CFR Part 46.

### 15.2 Institutional Review Board

The protocol, informed consent form(s), recruitment materials, and all participant materials have been submitted to the IRB for review and approval. Approval of both the protocol and the consent form must be obtained before any participant is enrolled. Any amendment to the protocol will require review and approval by the IRB before the changes are implemented to the study. All changes to the consent form will be IRB approved; a determination will be made regarding whether previously consented participants need to be reconsented.

### 15.3 Informed Consent Process

### 15.3.1 Consent/Assent and Other Informational Documents Provided to Participants

Consent forms describing in detail the study intervention, study procedures, and risks are given to the participant and written documentation of informed consent is required prior to starting intervention. The following consent

Version Date: September 27, 2019

materials are submitted with this protocol Informed Consent, audio consent for interview during the final study

visit.

#### 15.3.2 Consent Procedures and Documentation

Information will be obtained during screening for the study by the study team to determine eligibility. During screening, study staff will review the purpose, nature, risks, and benefits of the study; and determine eligibility. The period of time between recruitment and enrollment will be less than or equal to four weeks. This process will give the potential participant time to consider whether he/she wants to participate in the study. Participants will be reminded when the study is introduced, during recruitment and screening that participation is voluntary and that choosing not to participate in no way affects the quality or quantity of medical or nursing care provided to them. If at any point the candidate prefers not to proceed, the enrollment visit will be canceled. The candidate will be offered time after the in-person review of the consent form during the enrollment visit to think about her potential participation and to ask any questions before choosing to sign the study consent. In addition, participants are told that they may choose to withdraw from the study at any time.

Audio informed consents will be obtained for the fidelity checks and for the 30-minute audio-taped open ended interview during the final visit. As indicated above, participants will be reminded that participation is voluntary and that choosing not to participate in no way affects the quality or quantity of medical or nursing care provided to them. The candidate will be offered time after the in-person review of the consent form to think about her potential participation and to ask any questions before choosing to sign the study consent. In addition, participants are told that they may choose to withdraw from the study at any time.

Informed consent is a process that is initiated prior to the individual's agreeing to participate in the study and continues throughout the individual's study participation. Extensive discussion of risks and possible benefits of participation will be provided to potential participants. Consent forms will be IRB-approved and the participant will be asked to read and review the document. The investigator will explain the research study to the participant and answer any questions that may arise. All participants will receive a verbal explanation in terms suited to their comprehension of the purposes, procedures, and potential risks of the study and of their rights as research participants. The participant will sign the informed consent document prior to any procedures being done for the study. The participants may withdraw consent at any time throughout the course of the trial. A copy of the signed informed consent document will be given to the participants for their records. A copy of the signed informed consent document will be stored in the participant's research record. The consent process, including the name of the individual obtaining consent, will be thoroughly documented in the subject's research record. Any alteration to the standard consent process and the justification for such alteration will likewise be documented.

